# **Data Analysis and Statistics**

For each 30-min session, we will calculate SDT metrics of sensitivity (d') and criterion (c) using subjective reports of recognition as "yes" or "no". The d' indicates the ability to discriminate between real and scrambled images. It is computed by subtracting the z-transformed False Alarms Rate (FAR) from the z-transformed Hit Rate (HR): d' = Z(HR) - Z(FAR)), where Z is an inverse normal cumulative distribution function. The c represents the tendency to make "yes" reports to indicate recognition, regardless of whether the stimulus is a real or a scrambled image, which is computed as:  $c = 0.5 \times (Z(HR)+Z(FAR))$ . We will also calculate percent of correct responses as an operational measure of two alternative-forced-choice sensitivity using subjective category reports, i.e., responses to the first question: "Face" or "House".

For fMRI data, preprocessing steps will be implemented in AFNI (http://afni.nimh.nih.gov/afni). 1) Slice timing correction; 2) Rigid head motion correction/realignment within and across runs; frame-wise displacement (FD) of head motion was calculated using frame-wise Euclidean Norm (square root of the sum squares) of the six-dimension motion derivatives. A frame and its each previous frame will be tagged as zeros (ones, otherwise) if the given frame's derivative value has a Euclidean Norm above FD=0.5 mm; 3) Coregistration with high-resolution anatomical images; 4) Spatial normalization into Talairach stereotactic space and resampling to 3 × 3 × 3 mm³; 5) using AFNI's function 3dTproject, the time-censored data will be high-pass filtered above 0.008 Hz. Undesired components (e.g., physiological estimates, motion parameters) will be removed via linear regression. The latter include linear and nonlinear drift, time series of head motion, its temporal derivative, and mean time series from the white matter and cerebrospinal fluid; 6) Spatial smoothing with 6 mm full-width at half-maximum isotropic Gaussian kernel; 7) The time-course per voxel of each run will be normalized to zero mean and unit variance, accounting for differences in variance of non-neural origin (e.g., distance from head coil).

We will calculate the average BOLD activity (across the trials with real images) in the regions of interest including the CT, AIC, and DLPFC. For a given measurement, repeated-measures ANOVA plus post-hoc tests will be performed at the group level. Inter-subject multivariate linear regression analyses will be performed with SDT metrics as dependent variables and average BOLD activity as independent variables. Statistical significance will be defined at FDR-corrected  $\alpha < 0.05$ .

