Visual task. Participants will be asked to lay in the scanner, pay attention on the screen, and complete an image recognition task. All stimuli will be programmed using E-Prime (Psychology Software Tools, Pittsburgh, PA) and delivered via a visual presentation system designed for an MRI environment. Stimuli will be presented at the threshold of subjective recognition. An adaptive thresholding procedure will be conducted whereby image contrast will be titrated to reach a 50% subjective recognition rate for each subject. Stimuli will include two common visual object categories: faces and houses. Participants' task is to report the category ("F" or "H") of an image presented and their recognition experience ("Yes" or "No") (Fig. 3). Specifically, they will be instructed to report the object category regardless of their recognition experience and, in cases of unrecognized images, to make a genuine guess (two-alternative choice discrimination). Then, they will be instructed to report whether they see an object, such that even if the object appears unclear or noisy, they should respond "yes", but if they see nothing or only low-level features, such as cloud-like abstract patterns, they should respond "no".

**Fig. 3.** Visual task design. During each 30-min session, participants will complete an image recognition task. Stimuli (faces, houses, and scrambled images) will be presented at the threshold of subjective recognition. Participants' task is to report the category ("F" or "H") of the image presented and their recognition experience ("Yes" or "No").

The stimulus set will include real and scrambled images, where the scrambled images will be created by phase-shuffling a randomly chosen real image from each category to preserve category specific low-level image features [28]. Because scrambled images do not include an object stimulus, they are used as "catch trials" to determine the subjects' baseline tendency to give positive responses to a question about their recognition experience. Each object category will include four unique real images and one scrambled image. Each image will be repeated 10 times (i.e., trials) for each 30-min session. The pre-stimulus interval will vary randomly from trial to trial between 4 and 8 seconds to prevent stimulus timing predictability. The stimuli will be presented in a randomized order to prevent category predictability.

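### Percent correct on the Face/House report is labelled sensitivity, but it also depends on any preference for one category, which nothing in the plan measures

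*Combined protocol and SAP*

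**What the plan says.** The visual task (Experimental Design) shows one image per trial and asks two questions. The first is the category, F or H, answered on every trial; participants who do not recognise the image are told "to make a genuine guess (two-alternative choice discrimination"). The second is whether they saw an object, yes or no.

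On stimuli: "Each object category will include four unique real images and one scrambled image". On repetition: "Each image will be repeated 10 times (i.e., trials) for each 30-min session".

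Data Analysis and Statistics treats the two answers differently. For the second: "we will calculate SDT metrics of sensitivity (d') and criterion (c) using subjective reports of recognition". For the first: "We will also calculate percent of correct responses as an operational measure of two alternative-forced-choice sensitivity", obtained "using subjective category reports, i.e., responses to the first question". No d', criterion or other check on response preference is given for the category answer.

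Percent correct is not among the primary or secondary outcomes, and it does not appear under Anticipated Results and Interpretation or in the Power Analysis. The regressions take the signal detection metrics as dependent variables. Percent correct could enter only through the generically worded repeated-measures ANOVA.

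**The concern.** Percent correct is a fair stand-in for sensitivity when responses show no preference between the alternatives. With a single image per trial, nothing in the design forces that. A participant may lean towards one category, and the lean may differ between the awake, sedated and sedated-plus-LIFUP sessions.

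For the yes/no answer the plan separates willingness to respond from ability to discriminate. For the category answer it does not, and the yes/no c describes only the tendency to report recognition, so it cannot fill the gap.

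The category answer is the one planned behavioural measure not built on the yes/no report. A reader would naturally turn to it to ask whether sedation or LIFUP changed what was perceived or only what was reported. A shift in category preference could then be mistaken for a change in category discrimination.

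**Working it through.** The plan rests no sample size, power or error rate on percent correct, so there is no figure of its own to reproduce. The check asks how far percent correct moves when only preference changes.

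**Inputs from the documents.** Per session there are 2 categories × 4 real images × 10 repeats = 80 real-image trials (40 faces, 40 houses), and 2 × 1 × 10 = 20 scrambled trials.

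**Assumed inputs.** The documents give neither category discriminability nor category bias. I take category d' from 0 to 2.0 and bias b of 0, 0.25, 0.5 and 1.0 SD.

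**Model.** Equal-variance signal detection, as implied by the plan's own d' formula, with b > 0 meaning a lean towards F:

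- P(F given face) = Φ(d'/2 + b)
- P(H given house) = Φ(d'/2 − b)
- percent correct = ½[Φ(d'/2 + b) + Φ(d'/2 − b)]

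Example, d' = 1.5 and b = 1.0: ½[Φ(1.75) + Φ(−0.25)] = ½[0.960 + 0.401] = 68.1%. With b = 0 it is Φ(0.75) = 77.3%.

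| Category d' (assumed) | b = 0 | b = 0.25 | b = 0.5 | b = 1.0 | Fall in points at 0.25 / 0.5 / 1.0 |
|---|---|---|---|---|---|
| 0 | 50.0% | 50.0% | 50.0% | 50.0% | none |
| 0.5 | 59.9% | 59.6% | 58.7% | 56.0% | 0.3 / 1.2 / 3.9 |
| 1.0 | 69.1% | 68.6% | 67.1% | 62.1% | 0.5 / 2.0 / 7.0 |
| 1.5 | 77.3% | 76.6% | 74.7% | 68.1% | 0.7 / 2.6 / 9.2 |
| 2.0 | 84.1% | 83.4% | 81.2% | 73.9% | 0.7 / 2.9 / 10.2 |

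At d' = 1.5, a bias of 0.5 means keys split about 65:35, and 1.0 means about 78:22. Reading the biased score as unbiased, 2·Z(percent correct), gives an apparent d' of 1.33 and 0.94 respectively.

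**Against noise.** For one participant in one session of 80 trials, the sampling SD at 77.3% is √(0.773 × 0.227/80) = 4.7 points. For a group mean difference between two sessions, counting trial noise only, the standard error is √2 × 4.7/√25 = 1.3 points with 25 participants and √2 × 4.7/√100 = 0.7 with 100. Leaning either way lowers the score, so opposite preferences do not cancel. If biases are spread normally around zero with SD 0.5, mean percent correct at d' = 1.5 is Φ(0.75/√1.25) = 74.9%, about 2.5 points below the unbiased value.

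**The alternative measure.** Simulating 40 + 40 trials with a log-linear correction, mean category d' at biases 0, 0.5 and 1.0 is 1.00, 0.99 and 0.99 for a true value of 1.0; 1.49, 1.49 and 1.46 for 1.5; and 1.99, 1.98 and 1.91 for 2.0. It stays nearly constant where percent correct does not.

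**A contrasting model.** Suppose a fraction k of trials is fully known and the rest are pure guesses, with F guessed with probability g. Percent correct is k + (1 − k)[½g + ½(1 − g)] = k + ½(1 − k), whatever g is. With k = 0.5 it is 75%, whether guesses are even or all on one key.

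**The case against.** The strongest reply is that nothing planned depends on this measure. It is not a listed outcome, no hypothesis mentions it, and the predicted loss of stimulus differentiation is tied to the yes/no d', which is free of criterion under the same equal-variance model. That stands and limits the point to a supplementary measure.

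A reader might infer that favouring one key always lowers percent correct. The documents do not support that. Contrast is set to 50% recognition, real faces and houses are balanced, and participants guess when they recognise nothing, so bias confined to uninformed guesses is plausible and would leave the score unchanged. But the plan adopts signal detection theory, and percent correct alone cannot show which account applies.

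A stable preference creates no session effect; it must change between sessions. The randomised sham group also means that a shift common to all groups would not by itself look like a LIFUP effect. Both stand. The documents give no reason to expect such a change, and none to exclude it.

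The objection that a 2- to 3-point fall is below one participant's session noise is weaker, because the analyses are of groups.

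Scrambled trials are a separate matter. Scoring 20 of 100 trials at an assumed 50% would turn 77.3% into 0.8 × 77.3 + 0.2 × 50 = 71.9%, but that is a dilution, not a bias. The plan does not say these trials are scored. This is missing detail rather than a demonstrated error.

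**Conclusion.** The point holds in limited form. Percent correct on a one-image Face/House report mixes discrimination with category preference, and no planned quantity separates them. Under the plan's own model, with category d' of 1.0 to 2.0, the effect is negligible for mild bias, about 2 to 3 points for moderate bias and about 7 to 10 points for strong bias. All these sizes rest on assumed values.

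Two stronger readings should be resisted. One is that response bias will be reported as lost discrimination: it could be, but the plan announces no conclusion from percent correct. The other is that roughly a third of sensitivity could be lost spuriously: the drop from 1.5 to 0.94 (0.56/1.5 = 37%) is the strong-bias end of an assumed range, and no data in the documents point to it. The primary outcome and the listed c and d' are untouched.

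**What to change.** In Data Analysis and Statistics, state that the category answer is scored on real-image trials only, and add:

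- category d' = Z(P('F' given face)) − Z(P('F' given house))
- category criterion = ½[Z(P('F' given face)) + Z(P('F' given house))], the same form and sign as the plan's c
- a stated correction for rates of 0 or 1, for example log-linear

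Report these beside percent correct, and base any statement about Face/House sensitivity on category d'. Percent correct is worth keeping: if bias acts only on uninformed guesses, it is the steadier of the two, so showing both lets a reader see where they disagree.

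The cost is one extra supplementary measure and a small-sample correction, which pulls high values down slightly (simulated mean 1.91 for a true 2.0 at a bias of 1.0). The responses are already recorded. Listing category d' as a secondary outcome is optional.

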**Primary Outcome Measure:** Blood Oxygen Level Dependent (BOLD) response to visual stimuli (timeframe: baseline to 90 minutes).

**Secondary Outcome Measure:** Perceptual criterion (c) and sensitivity (d') derived from the Signal Detection Theory (SDT) (timeframe: baseline to 90 minutes).

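### Nuisance signals are regressed out before the trial responses are averaged, so any nuisance signal that tracks the task shrinks the primary BOLD measure, possibly by different amounts awake and sedated

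*Combined protocol and SAP*

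**What the plan says.** The primary outcome, listed at the end of Experimental Design, is the "Blood Oxygen Level Dependent (BOLD) response to visual stimuli (timeframe: baseline to 90 minutes"). It is an evoked response, not resting activity.

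Data Analysis and Statistics gives seven preprocessing steps. In step 5, "using AFNI's function 3dTproject, the time-censored data will be high-pass filtered above 0.008 Hz", and in the same step: "Undesired components (e.g., physiological estimates, motion parameters) will be removed via linear regression". Besides drift, the regressors named are "time series of head motion, its temporal derivative, and mean time series from the white matter and cerebrospinal fluid". Step 6 smooths the data. In step 7, "The time-course per voxel of each run will be normalized to zero mean and unit variance".

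The response measure comes only after these steps: "We will calculate the average BOLD activity (across the trials with real images") in the CT, AIC and DLPFC. It goes into a repeated-measures ANOVA with post-hoc tests, and into regressions with the signal-detection metrics as dependent variables.

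No first-level model with task and nuisance terms together is described. Nor is there a check of how far the nuisance series follow the task, or a sensitivity analysis on this step.

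**The concern.** When the data are residualised on the nuisance series first, those series take all the variance they share with the task, and a later trial average cannot recover it. If the nuisance series are unrelated to the task, little is lost. If they track it in part, some true response is removed.

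Overlap is plausible here. The Visual task text asks for two reports on every trial, which could bring small movements locked to the trial. White-matter and CSF averages can pick up stimulus-related signal from neighbouring tissue at the stated 3.4 x 3.4 x 4 mm resolution. Sedation could change either.

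The within-subject comparison of awake and sedated sessions is most exposed. Anticipated Results predicts lower BOLD activity in all three regions under sedation. A change in overlap between sessions could imitate or hide that result, and the same values feed the BOLD-SDT regressions.

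**Working it through.** The plan gives no figure for this point, so there is none to reproduce.

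**Inputs from the documents**
- Sampling interval 0.8 s (Imaging) and 30-minute sessions (Experimental Design): 30 x 60 / 0.8 = 2250 frames per session.
- Two categories, four real images and one scrambled image each, ten repeats (Visual task): 2 x 4 x 10 = 80 real and 2 x 1 x 10 = 20 scrambled trials.
- Nuisance set and order of steps as quoted above.

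**Assumed:** R2 in each session, response shape and noise model.

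**Algebra.** Let x be the task regressor after drift removal, y the voxel series, and M the operator that removes the nuisance series. The joint model gives b_joint = x'My / x'Mx. Residualising first and then measuring against x gives b_two = x'My / x'x. Since x'Mx = (1 - R2) x'x,

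b_two = b_joint x (1 - R2).

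The loss is 5% at R2 = 0.05, 10% at 0.10, 20% at 0.20 and 30% at 0.30.

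**Check by simulation.** 2250 frames, 100 trials, 14 autocorrelated nuisance series plus drift, 60 runs per setting, true response 1. One nuisance series tracks the task but does not otherwise drive the voxel.

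| R2 | Residualise, then fit | Residualise, then average trials | Joint model |
|---|---|---|---|
| 0.02 (chance) | 1.00 | 0.99 | 1.02 |
| 0.08 | 0.93 | 0.92 | 1.01 |
| 0.14 | 0.88 | 0.90 | 1.02 |
| 0.26 | 0.71 | 0.71 | 0.96 |
| 0.37 | 0.62 | 0.61 | 0.98 |

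The trial average, closest to what the plan describes, follows (1 - R2) within simulation error.

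**Awake against sedated.** Observed ratio = true ratio x (1 - R2 sedated) / (1 - R2 awake).
- R2 equal in both sessions: the ratio is unbiased. At 0.20 in both, a true fall of 0.20 of the awake response is measured as 0.80 x 0.20 = 0.16.
- 0.10 awake, 0.20 sedated, no true change: 0.80 / 0.90 = 0.89, an apparent fall of 11%.
- 0.20 awake, 0.05 sedated, no true change: 0.95 / 0.80 = 1.19, an apparent rise of 19%. A true 20% fall becomes 0.80 x 1.19 = 0.95, an apparent fall of 5%.

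**LIFUP against sham.** Suppose the groups share the same R2 in each session and the same mean response before LIFUP. The difference between groups in change from sedation to sedation with LIFUP is then (1 - R2 in the LIFUP session) x the true difference. It shrinks by a common factor, but no difference is created.

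**Limit of the joint model.** If the task-tracking nuisance series also shares noise with the voxel (loading 0.3), both methods are biased. At R2 of about 0.08, 0.15 and 0.27 the joint model gives 0.81, 0.74 and 0.59, against 0.74, 0.64 and 0.44 for residualising first. A separate run at R2 of 0.10 and 0.20 gave 0.71 and 0.56 jointly, against 0.63 and 0.44. An unchanged response with those two values awake and sedated would appear to fall by 1 - 0.56/0.71 = 21% jointly, and by 1 - 0.44/0.63 = 30% in the planned order.

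**The case against.** The strongest objection is that size and direction are unknown. The documents give no task-nuisance correlation for any session, and the loss is negligible at chance overlap. They do not say that head movement is locked to the trials, and step 2 tags frames above 0.5 mm, which limits the larger movements. This stands: the percentages above are illustrations over an assumed range.

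No trial-level estimator is named, so the absence of a joint model is inferred from the order of steps and the description of a plain average. It is the natural reading. The gap could also be closed by residualising the task regressors on the same nuisance set.

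The joint model is not a full cure. White-matter and CSF averages are removed because they are thought to share noise with grey matter, and in that case the joint estimate is biased too. It was nevertheless less biased than the planned order at every overlap above chance that was simulated.

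Step 7 puts the outcome in units of the residual standard deviation. The percentages here describe the response before that scaling, which is a separate matter.

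A reader might infer that the randomised comparison is compromised. The documents do not support this: all four groups, sham included, go through the same three sessions with the same task, so a shift in R2 caused by sedation should largely cancel. Only an effect of LIFUP itself on the overlap would break this, and the documents give no evidence of one.

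**Conclusion.** The point holds as a weakness in the order of analysis. As written, the plan multiplies the joint-model response by (1 - R2), a loss of 5% to 30% for assumed R2 of 0.05 to 0.30 and almost none at chance overlap. Unequal R2 would distort the awake-versus-sedated contrast and the BOLD-SDT regressions, in a direction that cannot be told in advance.

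A reader might go further and infer that a fall in BOLD under sedation would be an artefact, or that one joint model guarantees an unbiased answer. Neither follows. The first needs R2 values that the documents do not contain; the second fails when the white-matter and CSF averages both carry task signal and share noise with the voxel.

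The conclusion rests on reading the plan as having no joint model, and on the assumed R2 range. The change is worth making because it is cheap and addresses the primary outcome.

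**What to change.** For each session, fit one GLM containing real-image and scrambled-image regressors together with the listed motion, motion-derivative, white-matter, CSF and drift terms, with censored frames excluded. Name in advance one summary of the real-image response per region, and use it as the primary BOLD measure. Report the task-nuisance R2 by session, so that readers can see whether overlap differed between awake and sedated.

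Keep three sensitivity analyses:
- (a) the present pipeline of residualising and then averaging;
- (b) the joint model without the white-matter and CSF regressors, or with eroded masks, because the joint model reduces but does not remove the bias when those averages carry task signal;
- (c) a finite-impulse basis with a named summary window, in case propofol changes the response shape.

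The cost is SAP wording and analysis code; no new data are needed. Standard errors rise by roughly 10% to 30% at R2 of 0.10 to 0.30 in simulation (0.121 against 0.101 at 0.20, a ratio of 1.20). For a single regressor the algebra gives 1/(1 - R2), or 1.11, 1.25 and 1.43 at 0.10, 0.20 and 0.30. That is the same factor by which the estimate is restored, so little real information is lost. The finite-impulse version raised the SD by about a further 40% over the joint single-shape model at R2 of 0.10 to 0.20, and it yields many coefficients rather than one, so it should not be the required primary model.

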## **Experimental Design**

Three 30-min sessions will be conducted including wakeful baseline, moderate sedation, and the application of LIFUP under moderate sedation (sedation+LIFUP) with an effect-site concentrations of 1.5 µg/ml (Fig. 2). Moderate sedation will be achieved by IV infusion of propofol to achieve effect-site concentrations of 1.5 µg/ml. Infusion rate will be manually controlled. An initial bolus dose and subsequent infusion rate for each participant will be pre-determined based on a pharmacokinetic model [26] developed for target-controlled propofol infusion and implemented in software (STANPUMP [27]). A 5-min equilibration period between baseline and moderate sedation will be included. After sedation+LIFUP session, the infusion will be terminated allowing for spontaneous recovery of consciousness. A random group assignment will be applied in four groups of participants receiving LIFUP with sham control, or in the DLPFC, AIC, or CT, respectively.

[figure not shown]
[figure not shown]

Fig. 2. Concept, design and anticipated outcomes. In the hypothetical brain process (top left) visual

information propagates through ventral (V1/V2-->VOTC) and dorsal (V1/V2-->MTG-->PPC) pathways. The AIC receives inputs from the VOTC and prioritizes the inputs before sending them to the DLPFC for global broadcasting. The activities of DLPFC and AIC are hypothetically associated with two orthogonal SDT quantities, criterion (c) and sensitivity (d'). Given the wiring of the mesocircuit and thalamocortical loops (e.g., DLPFC-CT, and AIC-CT), the CT is hypothetically associated with the product of c and d'. Experimental design (bottom left) includes three fMRI sessions: wakeful baseline, moderate sedation, and LIFUP under moderate sedation. Participants will be assigned at random to four groups: those receiving LIFUP to DLPFC, AIC, CT or sham control. Anticipated effects are illustrated (right). Abbreviations: early visual cortex (V1/V2), ventral occipitotemporal cortex (VOTC), middle temporal gyrus (MTG), posterior parietal cortex (PCC).

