# **Anticipated Results and Interpretation**

We expect to observe a decrease of both c and d' during sedation, indicating more conservative responses and reduced stimulus differentiation. This would suggest that suppressing the state of consciousness diminishes the quality of conscious content. We also expect to find an overall reduction of average BOLD activity across all examined regions, i.e., in CT (state control), AIC (content gating) and DLPFC (content broadcasting). Furthermore, the change of c (baseline vs. sedation) may be associated with the change of DLPFC's average BOLD activity, and the change of d' may be associated with the change of AIC's average BOLD activity. The change of c × d' may be associated with the change of CT's average BOLD activity. Because the activity of CT supervenes on the activity of DLPFC and AIC, the state (CT) and contents (DLPFC/AIC) are altered together in sedation. If found, the results would suggest a neural mechanism for the linkage between state and contents. We also anticipate that the LIFUP stimulation in DLPFC during sedation will increase c without changing d' and increase the average BOLD activity in the

DLPFC. Stimulation of the AIC will increase d' without changing c, possibly through an enhancement of salience/attentional process offsetting the general inhibitory effect of propofol. Importantly, stimulation of the CT is expected to substantially increase both d' and c, arguably restoring perceptual performance to baseline level. This may be accompanied by an overall increase of average BOLD activity along the entire visual processing pathway.

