# **Power Analysis**

For an fMRI study of cognitive function, Desmond and Glover [29] reported that about 25 subjects are necessary to achieve 80% power for a 0.5% increase of activity. We also conducted power analysis based on our previous study with graded sedation of propofol [30]. The average Cohen's d as a measure of the effect size was 0.56. For 80% power and  $\alpha$ =0.05, N=24 human subjects will be needed. The obtained subject number is also very close to the suggested optimal group size for reliable statistics in functional MRI studies [31]. We plan for a minimum of 25 subjects per group.

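### Scaling each voxel to unit variance run by run mixes any session difference in signal SD into the baseline-versus-sedation BOLD contrast, and no common-scale analysis or SD check is planned

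*Combined protocol and SAP*

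**What the plan says.** Under Data Analysis and Statistics, preprocessing ends with step 7: "The time-course per voxel of each run will be normalized to zero mean and unit variance". The reason given is "accounting for differences in variance of non-neural origin (e.g., distance from head coil"; coil distance is the only example.

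Experimental Design sets out the conditions: "Three 30-min sessions will be conducted including wakeful baseline, moderate sedation, and the application of LIFUP under moderate sedation". The primary outcome is the "Blood Oxygen Level Dependent (BOLD) response to visual stimuli", with a timeframe covering all three sessions. It is averaged over real-image trials in the CT, AIC and DLPFC. Then "repeated-measures ANOVA plus post-hoc tests will be performed at the group level", and inter-subject regressions use "SDT metrics as dependent variables and average BOLD activity as independent variables".

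Anticipated Results and Interpretation predicts "an overall reduction of average BOLD activity across all examined regions" under sedation. It also links baseline-to-sedation changes in BOLD to changes in c, d' and their product.

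The plan does not define a run in relation to a session. The sections from Data Analysis and Statistics to Power Analysis plan no divisor common to sessions, no percent-signal scaling, no analysis without step 7 and no comparison of SD between sessions. The Anesthesia section asserts that propofol has little hemodynamic effect and so does not confound the fMRI results. That is not a check that the time-course SD is the same in each session.

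**The concern.** After step 7, a response is expressed relative to how much that voxel fluctuated in that run. If sedation changes the fluctuation, the scaled response moves even when the response itself does not.

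The stated rationale does not call for this. For a given voxel, distance from the coil is largely constant across a single visit, so one divisor per voxel and subject would deal with it. The SD left after step 5 cleaning also contains task response and spontaneous activity, so dividing by it does not remove only non-neural variance.

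Three results are exposed:
- the baseline-versus-sedation contrast, which is not randomised: every participant is sedated, so the sham group cannot separate an SD shift from an amplitude change;
- sedation versus sedation+LIFUP within a group;
- the change-versus-change associations in Anticipated Results and Interpretation.

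At stake is the predicted BOLD reduction. A fall in SD would shrink, hide or reverse it; a rise in SD would exaggerate it or create it. The criterion c, the sensitivity d' and the planned N are not affected.

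**Working it through.** **Inputs.** From the documents: step 7; three 30-minute sessions; TR 0.8 s, hence 30 × 60 / 0.8 = 2250 volumes; 2 categories × 4 real images × 10 repeats = 80 real trials per session; an average Cohen's "d as a measure of the effect size was 0.56"; N=24 stated, 25 per group and 100 in total planned. Assumed: every SD ratio, because none is given.

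**1. The plan's own figure.** The within-subject two-sided normal formula gives n = ((1.960 + 0.842)/0.56)² = 25.03, rounded up to 26; the two-sided paired t-test needs 28. The stated 24 is within 2 of the normal result. Two independent groups would need 51 per arm, so 24 is a within-subject calculation. Paired t-test power at N=25 is 76.6%.

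**2. Algebra.** Let r be the sedation SD divided by the baseline SD. The change read after step 7 is (response ratio)/r − 1.

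| r | No true change reads | True 20% fall reads |
|---|---|---|
| 0.8 | 1/0.8 − 1 = +25% | 0.8/0.8 − 1 = 0% |
| 0.9 | +11% | −11% |
| 1.1 | −9% | −27% |
| 1.2 | −17% | −33% |

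**3. Time-series check.** Simulated sessions had 2250 volumes, 80 real trials and the same raw response. Noise ratios of 0.8, 0.9, 1.1 and 1.25 moved the unit-variance response by +23.3%, +10.5%, −9.5% and −20.3%. The unscaled estimate moved by less than 1%.

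**4. Power to see a fall.** Assume that 0.56 is the baseline-versus-sedation effect on a common scale. The SD of the paired difference is then fall/0.56: 0.20/0.56 = 36%, 0.30/0.56 = 54% and 0.40/0.56 = 71% of the mean response. Run SDs are taken as log-normal (log-SD 0.106 in each session) with median ratio r. The test is a single two-sided 5% paired t-test, with 20,000 simulated trials per cell.

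| Analysis | N=25: fall 20/30/40% | N=100 pooled: fall 20/30/40% |
|---|---|---|
| Common scale | about 77% each | near 100% each (0.56 × √100 = 5.6 standard errors) |
| Unit variance, r=0.9 | 26/45/55% | 78/96/99% |
| Unit variance, r=0.8 | 3/16/31% | 3/50/86% |
| Unit variance, r=1.1 | 95/91/88% | not tabulated |

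At r=1.0, unit-variance power at N=25 is 71–75%.

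**5. False falls with no true change.** With r=1.1 and the same 36–71% range for the paired-difference SD, a significant fall appears in about 9–21% of trials at N=25 and 25–68% at N=100, against a nominal 2.5% in that direction. At r=1.0 total rejection is 5%. At r=0.9 the errors are false rises, and false falls occur in at most 1%. FDR correction across regions would lower both these rates and the power figures.

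**6. LIFUP versus sham, 25 per arm, no true effect.** Take the paired-difference SD as half the mean response. If r is the same in both arms, rejection stays at about 5%. If only the active arm's SD changes, it is about 10–12% at r=0.9 or 1.1.

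**7. Counter-case.** Suppose a session scales response and fluctuations together by 0.8 with the run mean fixed. Unit variance reads 0.8/0.8 − 1 = 0%; a common divisor or percent signal reads −20%. If the run mean scales too, as with receiver gain, percent signal also reads 0% and a common divisor still reads −20%.

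**The case against.** The strongest reply is that no harm has been shown. Nothing in the documents gives or implies a session SD ratio, and at a ratio of 1.0 step 7 costs only a few points of power and no excess error. This stands: every larger figure above depends on an assumed ratio.

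Second, the choice of scale is partly a choice of estimand. Coil distance is offered only as an example, and the counter-case shows that unit variance cancels a session-wide gain change with the run mean fixed, which neither alternative removes. This also stands. A reader might infer that step 7 is simply wrong and must be replaced in the primary analysis; the documents do not support that. What remains is that one scale alone cannot support a claim about amplitude.

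Third, the randomised comparison is LIFUP against sham. A reader might infer that it is biased as well. An SD shift shared by all arms leaves a null effect there at 0; only a target-specific SD change would bias it.

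Fourth, a reader might extend the concern to every regression of c and d' on BOLD. Within one session, scaling can usefully remove irrelevant differences between subjects. The concern is with the change-versus-change associations.

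Finally, Power Analysis does not say on what scale 0.56 was measured. If that was a unit-variance scale, the power loss in step 4 of the working does not follow, although the algebra does. Pooling all 100 participants also recovers most of the power at a ratio of 0.9.

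**Conclusion.** The concern holds as a cheap improvement. Provided no run spans two sessions, a session difference in SD is inseparable from an amplitude change in the three exposed results, and the plan has no means of detecting it. Its size and direction in this trial are unknown. Under the stated assumptions, a 10% SD difference shifts the reading by about 10 points. An SD ratio of 0.8 hides a true 20% fall completely, and pooling to N=100 does not rescue that case.

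A reader might go further and infer that the predicted reduction under sedation would be an artefact of scaling. The documents do not support this: only a rise in SD would falsely confirm the reduction, a fall would work against it, and no SDs are reported.

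**What to change.** - Define run in relation to session.
- Before data are seen, pre-specify a common-scale analysis of the session contrasts and change-score associations. Use either one divisor per voxel and subject for all three sessions, for example the cleaned baseline-run SD, or percent signal change from the stored run mean, applied after smoothing.
- Report it beside the unit-variance analysis, and state in advance which is primary. The sponsor may reasonably keep unit variance as primary if both are reported.
- Tabulate cleaned SD by session, region and group.
- Claim a sedation-related amplitude change only when the versions agree or the SD table explains the difference.

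The cost is a second analysis run, a small table and, for percent signal, a stored mean image. There are no new data and no change to N. The limitation is that neither common-scale version removes a gain change with the run mean fixed. The common divisor also leaves receiver gain in; percent signal removes it but leaves somewhat more scale variation between subjects and voxels.
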